### **Primary analysis in support of the European submissions**

Analysis of the primary endpoint will be conducted on the Off-treatment Hypothetical Estimand population based on treatment as randomized. The change from baseline to each postbaseline month in monthly migraine days will be analyzed using MMRM similar to the primary analysis specified for submission in the US. The analysis will be performed based on observed data collected from both double-blind treatment period and follow-up period.

#### **9.3.3 Sensitivity and Supplementary Analyses of the Primary Efficacy Endpoint**

Sensitivity analyses of the primary analysis of the primary efficacy endpoint are given below. Four sensitivity analyses and one supplementary analysis will be provided for the estimand in support of the submission in the US. In addition, copy-reference approach for sensitivity analysis will be provided for the estimand in support of the European submissions.

## **Sensitivity Analyses in Missing Data Handling**

### ANCOVA Model Based on 3-month Average of the Monthly Migraine Days

A supportive analysis will be performed on the primary endpoint using an ANCOVA model. The response variable for the ANCOVA model is the change from baseline in the calculated average monthly migraine days during the 12-week treatment period for each participant. The ANCOVA model includes treatment, region, number of classes of failed prior prophylactic treatments (2 and >2) as fixed factors, and baseline monthly migraine days as a covariate. The treatment difference for atogepant dose versus placebo will be estimated and reported along with the corresponding 95% CI and nominal p-value for superiority testing. There are no missing data for this analysis because participants who discontinued the treatment are assumed to maintain the same mean (observed while on treatment) for 3 months (12 weeks).

### Within-group Imputation Based on Observed Data

A Sensitivity analysis will be performed based on imputation using participants from the same treatment group with observed data under the MAR assumption. Missing data for participants who prematurely discontinued are assumed to copy the profile of participants in the same treatment group with observed data. The details of imputation are as follows:

1. Create partial imputation dataset using MI based on the MCMC approach in each treatment group. Imputed dataset will consist of 100 copies of original dataset and is assumed to follow monotone missing pattern.
2. Impute missing data in each existing copy by treatment group using observed data in the corresponding treatment group based on monotone regression. Each of the 100 imputed datasets will then be analyzed using an ANCOVA model with treatment, region, number of classes of failed prior prophylactic treatments (2 and > 2) as fixed factors, and baseline monthly migraine days as a covariate.
3. The ANCOVA analysis results from 100 completed datasets are combined for overall estimation and inference using Rubin's rule to produce a pooled estimate

of LS mean difference, its SE, and corresponding p-value for the test of null hypothesis of no treatment effect.

### Copy-Reference Approach

Copy-reference approach is one type of pattern-mixture models (PMM), under which data could be missing-not-at-random (MNAR), with repeated analyses combined via the reference based multiple imputation (MI) procedure. This approach is to assess the robustness of the MMRM analysis to possible violation of the missing-at-random (MAR) assumption in the primary analysis.

Step 1. A few intermittent missing values will be imputed by the Markov Chain Monte Carlo (MCMC) at first. The MCMC imputation assumes missing-at-random (MAR) for intermittent missing data. The MCMC method will be implemented using SAS Proc MI statement "MCMC impute=monotone." This is achieved with the use of option IMPUTE = MONOTONE in the MCMC statement. Then the rest of the missing data will follow monotone missing pattern.

Step 2. Implementation of the copy reference method are as follows:

1. The reference-based approach uses the placebo group as the reference. The missing values in the reference group are imputed using the observed data in that group under the missing-at-random assumption. The missing pattern is defined by the participant's last visit with a non-missing value. The mean vector and the covariance matrix of the multivariate normal distribution are estimated for reference group. The imputation of missing data is not based on each of the reasons of early termination, because there may not be sufficient non-missing efficacy data in each of the reason categories to serve as a stable reference.
2. For atogepant treatment group, missing values are imputed based on the distribution estimated from the reference group (placebo group).

The first PROC MI will be performed 100 times using MCMC method for partial imputation of the data with a non-monotone missing pattern. The output dataset will then be used as the input dataset for the next PROC MI. Note that the output dataset already contains 100 copies of the original dataset. With the next invocation of MI procedure, the missing data will be filled in (Step 1 and 2) for the existing copies. This is achieved with the use of NIMPUTE=1 and a BY \_Imputation\_ statement. Finally, each of the 100 imputed datasets will be analyzed using an analysis of covariance (ANCOVA) model. For a given imputed dataset, the average change from baseline in monthly migraine days is calculated across the 3 post-baseline months and is used as the response variable in the model. The model includes treatment group, region, number of classes of failed prior prophylactic treatments (2 and >2) as fixed factors, and baseline monthly migraine days as a covariate. The LS mean difference and corresponding SE is estimated from the model comparing each atogepant treatment group with the placebo group.

The ANCOVA analysis results from 100 completed datasets are combined for overall estimation and inference using Rubin's rule to produce a pooled estimate of LS mean difference, its SE, and corresponding p-value for the test of null hypothesis of no treatment effect.

### **Supplementary Analyses of the Primary Efficacy Endpoint**

The estimand in support of the European submissions will serve as one supplementary analysis of the primary efficacy endpoint for the estimand in support of the submission in the US, and vice versa.

### **Sensitivity Analysis for Possible Violation of Normality Assumption**

This sensitivity analysis uses MI in conjunction with robust regression to assess the robustness of the primary MMRM analysis to the possible violation of normality assumption. This method has been described and referred as ADAP [R]. The details of the method are as follows.

The normality test is performed on the residuals which are generated by the same MMRM as used for the primary efficacy analysis. The residuals are scaled by the inverse Cholesky root of its estimated variance-covariance matrix. The Kolmogorov-Smirnov test for normality is applied to the de-correlated and scaled residuals and normality test is rejected if p-value from the Kolmogorov-Smirnov test is less than 0.01.

If the normality test is rejected, sensitivity analysis below will be performed:

1. Create complete datasets using MI based on the Markov chain Monte Carlo (MCMC) approach. Imputed data will consist of 20 complete datasets.
2. Each of the 20 complete datasets will be analyzed using robust regression (M-estimation) to protect against either observed outliers in the original incomplete dataset, or imputed outliers in the completed datasets. For a given complete dataset, the average change from baseline in monthly migraine days is calculated across the 3 post-baseline months and is used as the response variable in the robust regression model. The model includes treatment group, region, number of classes of failed prior prophylactic treatments (2 and >2) as fixed factors, and baseline monthly migraine days as a covariate. The mean difference and corresponding SE are estimated from the model comparing atogepant treatment group with the placebo group.
3. The robust analysis results from 20 completed datasets are combined for overall estimation and inference using Rubin's rule to produce a pooled estimate of treatment difference, its SE, and corresponding p-value for the test of null hypothesis of no treatment effect.

## **9.4 Secondary Efficacy Endpoints and Analyses**

### **9.4.1 Secondary Efficacy Endpoints**

See Section [3.2](#).

## 9.4.2 Main Analyses of Secondary Efficacy Endpoints

The attributes of the estimands corresponding to the key secondary efficacy endpoints are summarized in [Table 5](#).

**Table 5. Summary of the Estimand Attributes of the Secondary Efficacy Endpoint**

Estimand Label	Attributes of the Estimand				
	Treatment	Endpoint	Population	Handling of Intercurrent Events	Statistical Summary
Secondary 1 in support of the submission in the US	Arm A: Placebo Arm B: Atogepant 60 mg QD Acute migraine medications as rescue medications are allowed to keep patients in the study	Achievement of at least a 50% reduction in mean monthly migraine days across the 12-week treatment period (yes/no)	mITT Population (see Section 4.0)	IE1: Regardless of whether allowed rescue medications are taken or not, data are included in the analysis. IE2: Data after the discontinuation from double-blind treatment period are excluded. The average of monthly migraine days is calculated for each participant based on available monthly migraine days during the double-blind period, and then the participant is dichotomized as a responder or non-responder.	The odds ratio in participants achieving at least a 50% reduction in 3-month average of monthly migraine days between atogepant group and placebo

Attributes of the Estimand					
Estimand Label	Treatment	Endpoint	Population	Handling of Intercurrent Events	Statistical Summary
Secondary 2 in support of the submission in the US	Arm A: Placebo Arm B: Atogepant 60 mg QD Acute migraine medications as rescue medications are allowed to keep patients in the study	Change from baseline in mean monthly headache days across the 12-week treatment period	mITT Population (see Section 4.0)	IE1: Regardless of whether allowed rescue medications are taken or not, data are included in the analysis. IE2: Data after the discontinuation from double-blind treatment period are excluded and assumed missing at random.	The difference in mean change from baseline in mean monthly headache days across the 12-week treatment period between atogepant group and placebo
Secondary 3 in support of the submission in the US	Arm A: Placebo Arm B: Atogepant 60 mg QD Acute migraine medications as rescue medications are allowed to keep patients in the study	Change from baseline in mean monthly acute medication use days across the 12-week treatment period	mITT Population (see Section 4.0)	IE1: Regardless of whether allowed rescue medications are taken or not, data are included in the analysis. IE2: Data after the discontinuation from double-blind treatment period are excluded and assumed missing at random.	The difference in mean change from baseline in mean monthly acute medication use days across the 12-week treatment period between atogepant group and placebo

Attributes of the Estimand					
Estimand Label	Treatment	Endpoint	Population	Handling of Intercurrent Events	Statistical Summary
Secondary 4 in support of the submission in the US	Arm A: Placebo Arm B: Atogepant 60 mg QD Acute migraine medications as rescue medications are allowed to keep patients in the study	Change from baseline in MSQ v2.1 Role Function Restrictive domain score at Week 12	mITT Population (see Section 4.0)	IE1: Regardless of whether allowed rescue medications are taken or not, data are included in the analysis. IE2: Data after the discontinuation from double-blind treatment period are excluded and assumed missing at random.	The difference in mean change from baseline in MSQ v2.1 Role Function Restrictive domain score at Week 12 between atogepant group and placebo
Secondary 5 in support of the submission in the US	Arm A: Placebo Arm B: Atogepant 60 mg QD Acute migraine medications as rescue medications are allowed to keep patients in the study	Change from baseline in mean monthly Performance of Daily Activities domain score of the AIM-D across the 12- week treatment period	mITT Population (see Section 4.0)	IE1: Regardless of whether allowed rescue medications are taken or not, data are included in the analysis. IE2: Data after the discontinuation from double-blind treatment period are excluded and assumed missing at random.	The difference in mean change from baseline in mean monthly Performance of Daily Activities domain score of the AIM-D across the 12-week treatment period between each atogepant group and placebo

Attributes of the Estimand					
Estimand Label	Treatment	Endpoint	Population	Handling of Intercurrent Events	Statistical Summary
Secondary 6 in support of the submission in the US	Arm A: Placebo Arm B: Atogepant 60 mg QD Acute migraine medications as rescue medications are allowed to keep patients in the study	Change from baseline in mean monthly Physical Impairment domain score of the AIM - D across the 12-week treatment period	mITT Population (see Section 4.0)	IE1: Regardless of whether allowed rescue medications are taken or not, data are included in the analysis. IE2: Data after the discontinuation from double-blind treatment period are excluded and assumed missing at random.	The difference in mean change from baseline in mean monthly Physical Impairment domain score of the AIM - D across the 12-week treatment period between each atogepant group and placebo

Attributes of the Estimand					
Estimand Label	Treatment	Endpoint	Population	Handling of Intercurrent Events	Statistical Summary
Secondary 1 in support of the European submissions	Arm A: Placebo Arm B: Atogepant 60 mg QD Acute migraine medications as rescue medications are allowed to keep patients in the study	Achievement of at least a 50% reduction in mean monthly migraine days across the 12-week treatment period (yes/no)	The Off-treatment Hypothetical Estimand Population (see Section 4.0)	IE1: Regardless of whether allowed rescue medications are taken or not, data are included in the analysis. IE2: Participants who start a new migraine prophylaxis treatment during the double-blind or safety follow-up period will have their data after starting the new migraine prophylaxis treatment during the follow-up period excluded from the analysis. IE3: Participants who discontinue study treatment due to all reasons other than starting a new migraine prophylaxis treatment will have their data collected after discontinuation of study treatment, and those off-treatment data will be included in the analysis. The average of monthly migraine days is calculated for each participant based on available monthly migraine days, and then the participant is dichotomized as a responder or non-responder.	The odds ratio in participants achieving at least a 50% reduction in 3-month average of monthly migraine days between atogepant group and placebo

Attributes of the Estimand					
Estimand Label	Treatment	Endpoint	Population	Handling of Intercurrent Events	Statistical Summary
Secondary 2 in support of the European submissions	Arm A: Placebo Arm B: Atogepant 60 mg QD Acute migraine medications as rescue medications are allowed to keep patients in the study	Change from baseline in mean monthly headache days across the 12-week treatment period	The Off-treatment Hypothetical Estimand Population (see Section 4.0)	IE1: Regardless of whether allowed rescue medications are taken or not, data are included in the analysis. IE2: Participants who start a new migraine prophylaxis treatment during the double-blind or safety follow-up period will have their data after starting the new migraine prophylaxis treatment during the follow-up period excluded from the analysis. IE3: Participants who discontinue study treatment due to all reasons other than starting a new migraine prophylaxis treatment will have their data collected after discontinuation of study treatment, and those off-treatment data will be included in the analysis.	The difference in mean change from baseline in mean monthly headache days across the 12-week treatment period between each atogepant group and placebo

Attributes of the Estimand					
Estimand Label	Treatment	Endpoint	Population	Handling of Intercurrent Events	Statistical Summary
Secondary 3 in support of the European submissions	Arm A: Placebo Arm B: Atogepant 60 mg QD Acute migraine medications as rescue medications are allowed to keep patients in the study	Change from baseline in mean monthly acute medication use days across the 12-week treatment period	The Off-treatment Hypothetical Estimand Population (see Section 4.0)	IE1: Regardless of whether allowed rescue medications are taken or not, data are included in the analysis. IE2: Participants who start a new migraine prophylaxis treatment during the double-blind or safety follow-up period will have their data after starting the new migraine prophylaxis treatment during the follow-up period excluded from the analysis. IE3: Participants who discontinue study treatment due to all reasons other than starting a new migraine prophylaxis treatment will have their data collected after discontinuation of study treatment, and those off-treatment data will be included in the analysis.	The difference in mean change from baseline in mean monthly acute medication use days across the 12-week treatment period between each atogepant group and placebo

Attributes of the Estimand					
Estimand Label	Treatment	Endpoint	Population	Handling of Intercurrent Events	Statistical Summary
Secondary 4 in support of the European submissions	Arm A: Placebo Arm B: Atogepant 60 mg QD	Change from baseline in the HIT-6 total score at Week 12	The Off-treatment Hypothetical Estimand Population (see Section 4.0)	IE1: Regardless of whether allowed rescue medications are taken or not, data are included in the analysis. IE2: Participants who start a new migraine prophylaxis treatment during the double-blind or safety follow-up period will have their data after starting the new migraine prophylaxis treatment during the follow-up period excluded from the analysis. IE3: Participants who discontinue study treatment due to all reasons other than starting a new migraine prophylaxis treatment will have their data collected after discontinuation of study treatment, and those off-treatment data will be included in the analysis.	The difference in mean Change from baseline in the HIT-6 total score at Week 12 between each atogepant group and placebo

Estimand Label	Attributes of the Estimand				
	Treatment	Endpoint	Population	Handling of Intercurrent Events	Statistical Summary
Secondary 5 in support of the European submissions	Arm A: Placebo Arm B: Atogepant 60mg QD Acute migraine medications as rescue medications are allowed to keep patients in the study	Change from baseline in MSQ v2.1 Role Function Restrictive domain score at Week 12	The Off-treatment Hypothetical Estimand Population (see Section 4.0)	IE1: Regardless of whether allowed rescue medications are taken or not, data are included in the analysis. IE2: Participants who start a new migraine prophylaxis treatment during the double-blind or safety follow-up period will have their data after starting the new migraine prophylaxis treatment during the follow-up period excluded from the analysis. IE3: Participants who discontinue study treatment due to all reasons other than starting a new migraine prophylaxis treatment will have their data collected after discontinuation of study treatment, and those off-treatment data will be included in the analysis.	The difference in mean Change from baseline in MSQ v2.1 Role Function Restrictive domain score at Week 12 between each atogepant group and placebo

The secondary endpoints for headache days, acute medication use days, Performance of Daily Activities domain score of the AIM-D, and Physical Impairment domain score of the AIM-D will be analyzed in the same manner as that used to analyze the primary endpoint. For MSQ v2.1 Role Function Restrictive domain score and HIT-6 total score, the analysis will be performed similarly to the primary MMRM, with focus on the pairwise contrasts of atogepant dose group to placebo at Week 12. Some participants may have MSQ v2.1 or HIT-6 assessed at Visit 8, which will not be included in MMRM

models. Note that the stratification of number of migraine days during the screening/baseline period (4 to  $< 8$  and  $\geq 8$ ) will be included in the secondary efficacy analyses if baseline values other than monthly migraine days are included in the corresponding models.

The 50% responder, defined as a participant with the achievement of at least a 50% reduction from baseline in the 3-month average of monthly migraine days, will be assessed for each participant. A logistic regression model will be used to analyze the 50% responders across the 12-week treatment period. This model assumes a binary distribution for the response and uses a logit link. The analysis model will include treatment group, region, the stratification of number of classes of failed prior prophylactic treatments (2 and  $>2$ ), and baseline monthly migraine days. The treatment difference in terms of odds ratio between each atogepant dose group and placebo will be estimated and tested from this model.

For the analyses in the mITT population, the 50% responder will be derived using data collected from the double-blind period. For the analyses in Off-treatment Hypothetical Estimand population, the 50% responder will be derived using data collected from the double-blind period and follow-up period; data after participants started a new prophylaxis treatment during the follow-up period will be excluded.

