6.7. Intervention after the End of the Study

No study intervention will be administered after the end of the study.

Following the end of study, the participant may be treated as per usual practice and standard of care or referred to the participant's treating physician/general practitioner for further medical care at the investigator's discretion.

7. Discontinuation of Study Intervention and Participant Discontinuation/Withdrawal

A premature discontinuation will occur if a participant who signs the ICF and receives study medication ceases participation in the study, regardless of circumstances, before the completion of the protocol-defined study procedures.

Participants may voluntarily withdraw from the study at any time. Notification of early participant discontinuation from the study and the reason for discontinuation will be made to the sponsor and will be clearly documented on the appropriate eCRF.

Participants can be prematurely discontinued from the study for one of the following reasons:

- Adverse Event
- Lack of efficacy
- Lost to follow-up
- Non-compliance with study drug
- Other
- Pregnancy
- Protocol deviation
- Site terminated by sponsor
- Study terminated by sponsor
- Withdrawal by subject

All randomized participants who prematurely discontinue from the study, regardless of cause, should be seen for final study assessments. The final assessments will be defined as completion of the evaluations scheduled for Visit 7/ET and Visit 8 EOS (Safety Follow-up Visit), 4 weeks post the last dose of study intervention. These participants must continue to complete their eDiary through Visit 8 EOS (Safety Follow-up Visit).

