9.6.6. Off-treatment Hypothetical Estimand Approach for the Secondary Endpoints

Continuous secondary endpoints will be handled using the same estimand approach defined above for the primary endpoint.

The secondary endpoint of 50% responders will be derived using both on-treatment and off-treatment observed data as defined in the primary endpoint above. The population-level summary for this endpoint is the odds ratio for each atogepant group relative to placebo.

10. Supporting Documentation and Operational Considerations

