10.8.4. Visit 7/Early Termination (Week 12)

- Effort should be made by the site to not schedule Visit 7 earlier than 12 weeks after Day 1 to ensure participants complete the full 12 weeks of treatment and have eDiary data through Day 83. Prior to any other test or evaluations, administer PRO measures, including: HIT-6, PGIC, PGI-S, WPAI:MIGRAINE, PSSM, MIDAS, MSQ v2.1, PROMIS-PI and PHQ-9.
- Review eDiary data and compliance.
- Complete Healthcare Resource Utilization Questionnaire
- Collect eDiary, only from participants who completed the double-blind treatment period (Visit 2 to Visit 7/ET; for participants who discontinue study, eDiary collection will occur at Visit 8)
- Perform physical examination.
- Perform urine pregnancy test for women of childbearing potential.
- Collect vital sign measurements (weight, pulse rate, respiratory rate, blood pressure, and body temperature).
- Assess C-SSRS on eTablet (the “Since Last Visit” assessment of the C-SSRS will be completed).
- Perform and transmit ECG.
- Update concomitant medications and procedures.
- Review and assess AEs.
- Collect blood and urine samples for chemistry, hematology, INR, and urinalysis.
- Collect post-dose PK sample (for participants who consented). The PK sample should be collected 1 to 10 hours post the daily dose.
- Collect previous visit study intervention, review participant compliance, and perform accountability.
- Access IWRS and enter accountability.
- Advise participants who early terminated from the double-blind treatment period to continue completing their eDiary through the Follow-up Visit. Remind participant to bring eDiary to next visit.

10.8.5. Visit 8 (End of Study) Week 16

- Prior to any other test or evaluations, administer PRO measures, including: EQ-5D-5L, HIT-6, and MSQ v2.1.
- Collect eDiary from participants who early terminated from the double-blind treatment period, review eDiary data and compliance.
- Perform physical examination.
- Assess C-SSRS on eTablet (the “Since Last Visit” assessment of the C-SSRS will be completed).
- Collect vital sign measurements (weight, pulse rate, respiratory rate, blood pressure, and body temperature).
- Perform urine pregnancy test for women of childbearing potential.
- Collect blood and urine samples for chemistry, hematology, INR, and urinalysis.
- Update concomitant medications and procedures.
- Review and assess AEs.
- Access IWRS to enter study visit.

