Objectives	Hypotheses	Estimands
To evaluate the effect of atogepant 60 mg QD and atogepant 60 mg QD versus placebo on physical impairment	Null hypothesis: atogepant 60 mg QD is equally effective to placebo in decreasing from baseline in mean monthly Physical Impairment domain score of the AIM-D across the 12-week treatment period  Alternative hypothesis: atogepant 60 mg QD is superior to placebo in decreasing from baseline in mean monthly Physical Impairment domain score of the AIM-D across the 12-week treatment period	Efficacy is to be measured using change from baseline in mean monthly Physical Impairment domain score of the AIM-D across the 12-week treatment period  The difference in mean Change from baseline in mean monthly Physical Impairment domain score of the AIM -D across the 12-week treatment period between atogepant group and placebo in the mITT Population. Data after the discontinuation from double-blind treatment period will be excluded and assumed missing at random (MAR).
For the European Union only: To evaluate the effect of atogepant 60 mg QD versus placebo on the impact of headaches on daily functioning as assessed by HIT-6	For the European Union only: Null hypothesis: atogepant 60 mg QD is equally effective to placebo in decreasing from baseline in the HIT-6 total score at Week 12  Alternative hypothesis: atogepant 60 mg QD is superior to placebo in decreasing from baseline in the HIT-6 total score at Week 12	Efficacy is to be measured using change from baseline in the HIT-6 total score at Week 12  The difference in mean change from baseline in the HIT-6 total score at Week 12 between atogepant group and placebo in the Off-treatment Hypothetical Estimand Population regardless of premature discontinuation of study drug. Data after starting a new migraine prophylaxis treatment use during the follow-up period will be excluded.

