## **9.5 Exploratory Efficacy Analyses**

For variables with a continuous response range, analyses will be performed similarly to that used for the primary analysis, with focus again on the pairwise contrasts of each dose group to placebo. Baseline in the primary MMRM model will be replaced with corresponding endpoint baseline. Note that the stratification of number of migraine days during the screening/baseline period (4 to  $< 8$  and  $\geq 8$ ) will be included in the additional efficacy analyses if baseline values other than monthly migraine days are included in the corresponding models. There is only one post-baseline assessment for MIDAS and PHQ-9, and thus ANCOVA model will be used to analyze MIDAS and PHQ-9 related endpoints with model terms including treatment group, region, the stratification of

number of classes of failed prior prophylactic treatments (2 and >2), number of migraine days during the screening/baseline period (4 to < 8 and  $\geq$  8) and corresponding baseline score. For the endpoints change from baseline in HIT-6, MSQ 2.1 and EQ-5D-5L descriptive system index score and vas score, Week 16 (follow up visit) will not be included in MMRM model fitting. Only descriptive statistics for Week 16 will be provided.

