**Table 13. Item Values for HIT-6 Item Responses**

Response Categories	Precoded Item Value	Final Item Value
Never	0	6
Rarely	1	8
Sometimes	2	10
Very Often	3	11
Always	4	13

The HIT-6 instrument has a recall period of 4 weeks for 3 of the 6 items.

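### EU analysis of HIT-6 (S4) and MSQ (S5) is labelled off-treatment, but SAP 9.4.2 drops every Visit 8 score, the main off-treatment record

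*SAP*

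**What the plan says.** **The EU estimand.** In SAP Table 5, EU Secondary 4 (HIT-6 at Week 12) and Secondary 5 (MSQ Role Function-Restrictive at Week 12) carry the same rule: participants who stop study treatment for any reason other than starting a new prophylactic "will have their data collected after discontinuation of study treatment, and those off-treatment data will be included in the analysis". SAP 2.1 defines both effects in the "Off-treatment Hypothetical Estimand Population regardless of premature discontinuation of study drug". Protocol 9.6.6 agrees: "Continuous secondary endpoints will be handled using the same estimand approach defined above for the primary endpoint". For the EU primary, SAP 9.3.2 uses observed data from both the double-blind and follow-up periods.

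**The EU analysis.** SAP 9.4.2 has one sentence on these scales at follow-up: "Some participants may have MSQ v2.1 or HIT-6 assessed at Visit 8, which will not be included in MMRM" models. It separates neither EU from US nor early terminators from completers. SAP 9.5 treats the follow-up visit as Week 16, keeps it out of model fitting and adds: "Only descriptive statistics for Week 16 will be provided".

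**What is collected.** Protocol 7.1 makes stopping study drug also mean leaving the study. Under Protocol Section 7, the final assessments are then the "evaluations scheduled for Visit 7/ET and Visit 8 EOS (Safety Follow-up Visit), 4 weeks post the last dose of study intervention". Both visits include the two scales; for Visit 8, Protocol 10.8.5 says: "Prior to any other test or evaluations, administer PRO measures, including: EQ-5D-5L, HIT-6, and MSQ v2.1".

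**The concern.** Table 5 and SAP 9.4.2 give opposite instructions for the same records. If 9.4.2 is followed, post-discontinuation values for EU S4 and S5 are mostly absent and are handled by the MMRM as missing at random. That is essentially the US on-treatment analysis under an off-treatment label.

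HIT-6 and MSQ are the fourth and fifth secondary endpoints in the EU fixed sequence (SAP Table 7), so each can support a type-I-controlled claim. At stake is which treatment effect that claim describes.

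**Working it through.** **1. Power is not the issue.** Inputs from SAP 2.4 and Table 2: 150 per arm, 15% dropout, two-sided alpha 0.05; HIT-6 difference 3.9, SD 7.6; MSQ difference 10.9, SD 22.8. Evaluable n = 150 × 0.85 = 127.5 per arm. Power ≈ Φ(δ / (SD × √(2/n)) − 1.96).

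- HIT-6: 3.9 / (7.6 × √(2/127.5)) = 4.10, giving 98.4% (plan: 98%).
- MSQ: 10.9 / (22.8 × √(2/127.5)) = 3.82, giving 96.8% (plan: 96%).

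Both figures reproduce. The Table 2 footnote says the EU differences were already obtained with the off-treatment approach.

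**2. Why Visit 8 is the main off-treatment record.** MSQ has a 4-week recall (SAP Appendix B), and for the other scale "The HIT-6 instrument has a recall period of 4 weeks for 3 of the 6 items". If ET takes place g days after the last dose, the share of a 28-day recall spent on drug is (28 − g)/28: 100% for g = 0, 75% for g = 7, 50% for g = 14. The documents do not state g. At Visit 8, nominally 28 days after the last dose, the recall falls off drug.

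**3. Visit 8 is not always Week 16.** For completers it is, and excluding it from a Week 12 contrast is sensible. For early terminators, Visit 8 day = stop day + 28. Someone stopping on Day 56 has Visit 8 at about Day 84, which is Week 12. The EU primary can use that participant's eDiary data for Days 57 to 84, while the Day 84 HIT-6 and MSQ scores are discarded.

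**4. How many records.** Maximum per arm: 0.15 × 150 = 22.5, if all dropouts attend Visit 8. Assume stop days uniform over Days 1 to 83, so Visit 8 falls on Days 29 to 111, and assign each score to the nearest of Days 28, 56 and 84. The Week 12 upper limit is either Day 87 (the +3-day Visit 7 window) or Day 98 (84 + 14).

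| Visit 8 falls on | Share | Per arm |
|---|---|---|
| Days 29–42 (Week 4) | 14/83 = 16.9% | 3.8 |
| Days 43–70 (Week 8) | 28/83 = 33.7% | 7.6 |
| Days 71–87 (Week 12, narrow) | 17/83 = 20.5% | 4.6 |
| Days 71–98 (Week 12, wide) | 28/83 = 33.7% | 7.6 |
| After Day 98 | 13/83 = 15.7% | 3.5 |

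The two Week 12 rows are alternatives. With stopping weighted linearly toward early days, the Week 12 share is 16.1% to 22.1% (3.6 to 5.0 per arm); toward late days, 24.9% to 45.4% (5.6 to 10.2). If only half attend Visit 8, every count halves.

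**5. Duplicates.** Taking ET as the stop day, ET and Visit 8 share a nearest window only for stop days 1 to 14 (both in Week 4): 14/83 = 16.9%. A rule for two records in one window is therefore needed.

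**6. Does another section settle it?** SAP Section 8 extends the primary's handling only to continuous secondaries collected by eDiary; SAP Table 9 lists HIT-6 and MSQ as eTablet. SAP 15.1 lists only the 14-day diary rule and the subgroups as changes from the protocol. Within 9.4.2 itself, the 50% responder endpoint does get separate US and EU data rules; these two scales do not.

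**The case against.** The strongest reply is that the exclusion is deliberate. The SAP's version history records that Visit 8 HIT-6 and MSQ data are for descriptive statistics only. SAP 9.4.2 and 9.5 agree, the Section 8 rule is limited to eDiary endpoints, and SAP 2.2 mentions only eDiary data for early terminators in follow-up. On this reading the Table 5 text was carried over from the diary endpoints, and a programmer would know what to do. Protocol 9.6.4 also leaves detailed methods to the SAP.

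Intent is a fair point, but it does not reconcile the passages: Table 5 and SAP 2.1 still define an estimand that the analysis does not target. If on-treatment handling is what is wanted, those sections are what need changing.

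Three further points stand in part:

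- **Some off-treatment data may remain.** An ET score taken after the last dose could enter the EU model, so the overlap with the US data is close rather than complete. The SAP gives no rule mapping ET scores to analysis weeks.
- **Remapping recovers only part of Week 12.** With uniform stopping, those who stop on Days 1 to 42 (42/83 = 51%, about 11 of 22 per arm) have Visit 8 by Day 70 and still have no Week 12 score. With the Day 87 limit, those stopping on Days 60 to 70 also have none, making 53/83 = 64%, about 14 of 22. Their Week 4 or Week 8 scores would contribute only through the model.
- **Nothing in the planning figures points to a large shift.** MSQ is 10.8 (SD 22.6) in the US table and 10.9 (SD 22.8) in the EU table, although the documents do not say whether Visit 8 scores entered the EU figure. In an extreme illustration where all 15% contribute a score with no retained effect, the differences fall to about 3.3 (3.9 × 0.85) and 9.3 (10.9 × 0.85), with power still 96.5% and 94.1%.

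These points limit the likely numerical effect. They do not remove the mismatch.

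**Conclusion.** The concern holds and should be fixed. For EU S4 and S5, the stated estimand includes post-discontinuation data and the analysis removes the main source of it. The conflict concerns early terminators only, and excluding completers' Week 16 scores is right.

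The ceiling of about 22 per arm rests on the planned 15% dropout and full Visit 8 attendance; loss to follow-up, withdrawal or new prophylaxis lowers it. The 5 to 8 per arm in a Week 12 window (3% to 5% of 150) assumes uniform stopping; early- or late-weighted stopping widens this to about 4 to 10. The effect on the estimates cannot be quantified or signed from the documents.

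**What to change.** Choose one and make the SAP consistent.

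1. **Keep the off-treatment estimand.** In the EU HIT-6 and MSQ models, assign early terminators' ET and Visit 8 scores to Week 4, 8 or 12 by actual study day. State the windows (for example, nearest target day with an upper limit for Week 12) and a rule for two scores in one window (for example, keep the one closest to the target day). Apply the new-prophylaxis exclusion already in Table 5. Limit the Visit 8 exclusion in 9.4.2 to participants who completed Week 12, and align the Week 16 wording in 9.5.
2. **Keep the exclusion.** Restate EU S4 and S5 in Table 5 and SAP 2.1 as on-treatment estimands with data after discontinuation assumed missing at random, and list this in SAP 15.1 as a change from Protocol 9.6.6.

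The first costs SAP wording and a small visit-window derivation on data already collected, and may move the two EU estimates slightly in either direction. The second costs wording only.
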